#### 5.6.2.1 MR Severity at 12 Months

Subjects in the Device group are expected to experience greater reduction in MR severity than subjects in the Control group.

#### **Hypothesis:**

The null and alternative hypotheses are stated as:

**H**0: 
$$P_{D,MR \le 2^+} - P_{C,MR \le 2^+} = 0$$
 vs.

**H**1: 
$$P_{D, MR \le 2^+} - P_{C, MR \le 2^+} \ne 0$$

where  $P_{D, MR \le 2^+}$  and  $P_{C, MR \le 2^+}$  represent the proportion of subjects with MR severity  $\le 2^+$  at 12 months in the Device and Control groups, respectively.

Fisher's exact test at the 5% level of significance will be used to compare the proportion of subjects in the Device and Control groups with MR severity  $\leq$  2+ at 12 months. As a sensitivity analysis, for subjects who experience an adjudicated heart failure death prior to completing 12 months follow-up, these subjects will be classified with MR of severity 4+ in the analysis. This sensitivity analysis is exploratory and Type I error control does not apply to these hypotheses.

# 5.6.2.2 Change in Six-Minute Walk Test Distance (6MWD) at 12 Months over Baseline

Improvement in the 6MWD at 12 months from baseline is an important secondary effectiveness endpoint in the comparison of the Device group to the Control group.

#### **Hypothesis:**

The null and alternative hypotheses are stated as:

 $\mathbf{H_0}$ :  $\mu_{T,\Delta 6MWD} - \mu_{C,\Delta 6MWD} = 0$  vs.

**H**1:  $\mu$ T,Δ6MWD -  $\mu$ C,Δ6MWD  $\neq$  0

where  $\mu_{T,\Delta6MWD}$  and  $\mu_{C,\Delta6MWD}$  represent the mean change in distance walked between 12 months and baseline in the Device and Control groups respectively.

The analysis will be performed in subjects with paired 6MWD data at baseline and 12 months. Subjects who experience adjudicated heart failure death prior to completing 12 months follow-up or are unable to exercise due to cardiac reasons will also be included in the analysis. These subjects will be assigned 6MWD of 0 meters at 12 months in the analysis.

Analysis of covariance (ANCOVA) will be used to compare the mean changes in 6MWD between 12 months and baseline in the two groups, while adjusting for baseline 6MWD value. Least squares means (LS-Means) and 95% confidence interval for the change in 6MWD between 12 months and baseline will be calculated for the Device and Control groups, respectively.

A two-sample t-test and a Wilcoxon Rank Sum test will be conducted as supplementary analyses.

In addition to a significant p-value for this analysis, the point estimate of the difference in mean improvement between the two groups (Device-Control) should be at least 24 meters to meet this endpoint.

# 5.6.2.3 Change in Quality of Life (Kansas City Cardiomyopathy Questionnaire, KCCQ) at 12 Months over Baseline

Improvement in quality of life as measured by the KCCQ Test at 12 months from baseline will be a secondary effectiveness endpoint in the comparison of the Device group to the Control group.

#### **Hypothesis:**

The null and alternative hypotheses are stated as:

 $\mathbf{H_0}$ :  $\mu_{D,\Delta KCCQ} - \mu_{C,\Delta KCCQ} = 0$  vs.

 $\mathbf{H}_1$ :  $\mu_{D.\Delta KCCO} - \mu_{C.\Delta KCCO} \neq 0$ 

where  $\mu_{D,\Delta KCCQ}$  and  $\mu_{C,\Delta KCCQ}$  represent the mean change in quality of life score between 12 months and baseline in the Device and Control groups respectively.

The analysis will be performed in subjects with paired KCCQ score data at baseline and 12 months. Subjects who experience an adjudicated heart failure related cardiovascular death prior to completing 12 months follow-up will also be included in the analysis. These subjects will be assigned the lowest KCCQ score at 12 months observed for any subject in the analysis. The lowest possible KCCQ score is 0 point.

ANCOVA will be used to compare the mean changes in KCCQ score between 12 months and baseline in the two groups, while adjusting for baseline KCCQ score. LS-Means and 95% confidence interval for the change in KCCQ score between 12 months and baseline will be calculated for the Device and Control groups, respectively.

A two-sample t-test and a Wilcoxon Rank Sum test will be conducted as supplementary analyses.

In addition to a significant p-value for this analysis, the point estimate of the difference in mean improvement between the two groups (Device-Control) should be at least 5 units to meet this endpoint.

## 5.6.2.4 Change in LVEDV at 12 Months over Baseline

Reduction in MR severity with the MitraClip device is expected to be associated with reduction in LVEDV.

#### **Hypothesis:**

The null and alternative hypotheses are stated as:

 $\mathbf{H_0}$ :  $\mu_{D.\Delta LVEDV} - \mu_{C.\Delta LVEDV} = 0$  vs.

 $H_1$ :  $\mu_{D,\Delta LVEDV}$  -  $\mu_{C,\Delta LVEDV} \neq 0$ 

where  $\mu_{D,\Delta LVEDV}$  and  $\mu_{C,\Delta LVEDV}$  represent the mean change in left ventricular end diastolic volumes at 12 months over baseline in the Device and Control groups, respectively.

All subjects with paired LVEDV data at baseline and 12 months will be included in the analysis. Subjects who experience an adjudicated heart failure death prior to completing 12 months follow-up will also be included in the analysis. These subjects will be assigned the worst LVEDV change at 12 months from baseline observed for any subject in the analysis.

ANCOVA will be used to compare the mean changes in LVEDV between 12 months and baseline in the two groups, while adjusting for baseline LVEDV score. LS-Means and 95% confidence interval for the change in LVEDV between 12 months and baseline will be calculated for the Device and Control groups, respectively.

A two-sample t-test and a Wilcoxon Rank Sum test will be conducted as supplementary analyses.

#### 5.6.2.5 NYHA Functional Class I or II at 12 months

Reduction in MR severity with the MitraClip device is expected to be associated with higher proportion of NYHA Functional Class I or II at 12 months in the Device group.

The null and alternative hypotheses may be stated as:

 $\mathbf{H_0}$ :  $\mathbf{P_{D,NYHA\ I/II}} - \mathbf{P_{C,NYHA\ I/II}} = \mathbf{0} \text{ vs.}$ 

 $\mathbf{H_1}$ :  $\mathbf{P_{D,NYHA}}$  I/II -  $\mathbf{P_{C,NYHA}}$  I/II  $\neq 0$ 

where PDNYHA I/II and PCNYHA I/II represent the proportion of subjects with NYHA Class I/II at 12 months in the Device and Control groups, respectively.

Fisher's exact test at the 5% level of significance will be used to compare the proportion of subjects in the Device and Control groups with NYHA Class I/II at 12 months.

All subjects with NYHA data at 12 months will be included in the analysis. Subjects who experience an adjudication heart failure death prior to completing 12 months follow-up will also be included in the analysis. These subjects will be assigned a 12-month NYHA class of IV.

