 - b) revascularization and/or implant of Cardiac Resynchronization Therapy device (CRT or CRT-D) or reprogramming of an implanted CRT or CRT-D that results in increased biventricular pacing (from $<92\%$ to $\geq 92\%$)
4. New York Heart Association (NYHA) Functional Class II, III or ambulatory IV.
 5. The Local Site Heart Team (CT surgeon and HF specialist investigators) and the Central Eligibility Committee concur that surgery will not be offered as a treatment option and that medical therapy is the intended therapy for the subject, even if the subject is randomized to the Control group.
 6. Left Ventricular Ejection Fraction (LVEF) is $\geq 20\%$ and $\leq 50\%$ within 90 days prior to subject registration, assessed by the site using any one of the following methods: echocardiography, contrast left ventriculography, gated blood pool scan or cardiac magnetic resonance imaging (MRI).

Note: The method must provide a quantitative readout (not a visual assessment).

7. Left Ventricular End Systolic Dimension (LVESD) is ≤ 70 mm assessed by site based on a transthoracic echocardiographic (TTE) obtained within 90 days prior to subject registration.
8. The primary regurgitant jet is non-commissural, and in the opinion of the MitraClip implanting investigator can be successfully be treated by the MitraClip. If a secondary jet exists, it must be considered clinically insignificant.
9. Creatine Kinase-MB (CK-MB) obtained within prior 14 days $<$ local laboratory ULN (Upper Limit of Normal)
10. Transseptal catheterization and femoral vein access is determined to be feasible by the MitraClip implanting investigator.
11. Age 18 years or older.

12. The subject or the subject's legal representative understands and agrees that should he/she be assigned to the Control group, he/she will be treated with medical therapy and conservative management without surgery and without the MitraClip, either domestically or abroad. If the subject would actively contemplate surgery and/or MitraClip if randomized to Control, he/she should not be registered in this trial.
13. The subject or the subject's legal representative has been informed of the nature of the trial and agrees to its provisions, including the possibility of randomization to the Control group and returning for all required post-procedure follow-up visits, and has provided written informed consent.

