- The following tests must be performed by a coordinator who will not be involved in day-to-day activities of the COAPT trial and will not have access to the eCRFs. This coordinator will be designated as “blinded” study personnel, and will not have knowledge of the subject’s treatment assignment. A standardized script will be used when administering these assessments:
 - KCCQ and SF-36 QoL questionnaires must be completed by the subject;
Note: To minimize bias and undue influence, the QoL questionnaires will be completed by the subject, unless the subject is unable to complete the questionnaire on their own (in such cases a note to file must be completed to document the inability of subject to complete the questionnaire).

¹⁵ Fried LP, Tangen CM, Waltson J et al. Frailty in older adults: Evidence for a phenotype. *J Gerontol A Biol Sci Med Sci.* 2001 56:M146-M156.

- The 6-Minute Walk Test (6MWT) must be administered according to the ATS Statement: Guidelines for the Six-Minute Walk Test, Official Statement of the American Thoracic Society, approved March 2002 (See **APPENDIX E: 6 Minute Walk Test Guidelines**).
- An assessment of NYHA Functional Class must be completed.

The following screening and baseline information must be captured on the appropriate electronic Case Report Forms (eCRFs):

- Inclusion and Exclusion criteria
- Demographics (e.g., date of birth, gender, race/ethnicity)
- Informed Consent date

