6.7 Randomization

Before randomization:

- Echocardiography Core Lab must confirm MR severity
- Eligibility Committee must confirm that the subject is on optimal therapy including GDMT and is not appropriate for mitral valve surgery according to local site standards either at baseline or if the subject deteriorates and/or MR increases in severity during follow-up
- Site must reconfirm that subject meets eligibility criteria after Eligibility Committee approval and all baseline tests and assessments must be completed (within 14 prior to randomization)

If screening TEE shows intracardiac mass, thrombus or vegetation, or the Eligibility Committee determines subject requires additional treatment before consideration for the trial, the subject may be deferred and reconsidered for the trial, at which time the TEE must be repeated.

Subjects will be randomized or assigned as a roll-in through the eCRF database. The following baseline information must be captured for registered subjects on the appropriate eCRFs:

- Subject medical history and risk factors
- Current cardiovascular medications
- Physical measurements and vital signs (e.g. weight, height, heart rate, blood pressure and temperature)

6.8 “Treatment” Visit (Device Group or Roll-in Subjects)

For Device group or roll-in subjects, the MitraClip procedure will be performed during the “Treatment” visit. For randomized subjects, the MitraClip procedure must be completed between 1 and 14 days after randomization.

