#### 5.3 Demographic and Baseline Characteristics

The Device and Control groups will be compared with respect to demographic and baseline characteristics. The two groups are expected to be well balanced at baseline due to randomization. Comparisons will be made with respect to age, sex, race and ethnicity, cardiovascular conditions, diabetes, renal disease, prior MI, prior stroke, NYHA Class, previous cardiac surgery, prior HF hospitalization, LVEF, left ventricular size, creatinine levels, STS mortality risk score, MR severity, KCCQ score, 6-minute walk distance and baseline medications. Continuous variables will be analyzed using the t-test or using non-parametric methods and categorical variables will be compared using Fisher's Exact test.

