#### 5.8.4.1 Change in KCCQ QoL score at 12 Months

A simulation was performed. Based on the following assumptions, the power is > 90% to reject the null hypothesis at the 5% significance level.

- Subjects in the Device group have 8 points more improvement in the mean change of KCCQ score at 12 months from baseline than subjects in the Control group, with standard deviation (SD) of 25 points for the mean change in KCCQ score in each group.
- Assume all-cause mortality rate at 12 months is 27% in the Control group, and 22% in the Device group. Approximate 70% of all-cause deaths in each group are due to cardiovascular reasons. Furthermore, about 70% of cardiovascular deaths are HF related. Thus, it is expected to have approximate 3% difference in HF related cardiovascular deaths at 12 month between two treatment groups (i.e. 10% in the Device group and 13% in the Control group). Subjects who experienced heart failure death prior to 12 months follow-up are assigned with the lowest KCCQ score at 12 months

- 10% attrition rate in both groups due to withdrawn or missed visit at 12 months.
- Two-sample t-test (it is anticipated that an ANCOVA analysis adjusting for baseline values provides as much as or more power than a two-sample t-test  $^{9,10}$ ).

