#### 5.8.4.5 NYHA Functional Class of I/II at 12 months

Sample size calculation for the NYHA Functional Class I/II at 12 months was performed using NCSS PASS 11 (Hintze, J., 2011, NCSS, LLC. Kaysville, Utah).

The power calculation for the NYHA Functional Class I/II rate at 12 months is based on the following assumptions:

- Assume 60% of subjects in the Control group had NYHA Functional Class I/II at 12 months, and 75% of subjects in the Device group had NYHA Functional Class I/II at 12 months. Thus, there is 15% more NYHA Functional Class of I/II at 12 months in the Device group than those in the Control group.
- Assume all-cause mortality rate at 12 months is 27% in the Control group, and 22% in the Device group. Approximate 70% of all-cause deaths in each group are due to cardiovascular reasons. Furthermore, about 70% of cardiovascular deaths are HF related. Thus, it is expected to have approximate 3% difference in HF related cardiovascular deaths at 12 month between two treatment groups (i.e. 10% in the Device group and 13% in the Control group). Subjects who experienced heart failure death prior to 12 months follow-up are assigned with NYHA Functional Class IV at 12 months.
- 10% attrition rate in both groups due to withdrawn or missed visit at 12 months.
- Fisher's exact test

With the effective sample size of approximate 220 subjects in each arm at 12 months, there is approximate 90% power to demonstrate that there are more subjects in the Device group who had NYHA Functional Class I/II at 12 months than those in the Control group.

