#### 5.9 Multiplicity Adjustments

Both the primary safety and primary effectiveness endpoints must be met for trial success.

The secondary endpoints will be evaluated for labeling claims if both primary endpoints are met. The secondary endpoints will be tested sequentially in the following order:

- MR Severity of  $\leq 2+$  at 12 months
- All-Cause Mortality at 12 months (Non-inferiority test)
- Hierarchy of death and recurrent HF hospitalization (analyzed when the last subject completes 12 months of follow-up)
- Change in KCCQ score at 12 months from baseline
- Change in 6MWD at 12 months from baseline
- Recurrent hospitalizations all-cause (analyzed when the last subject completes 12 months of follow-up)
- NYHA Functional Class of I/II at 12 months
- Change in Left Ventricular End Diastolic Volume at 12 months
- All-Cause Mortality (Superiority test, if HR < 1) (analyzed when the last subject completes 12 months of follow-up and use all available data up to 24 months)
- Composite 30-Day Secondary Safety Endpoint

The multiplicity adjustments above are only performed for the primary analyses (ITT) of the primary and secondary endpoints.

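### The Fisher's exact tests for NYHA I/II and MR ≤2+ at 12 months are valid and adequately powered, but a stratified Cochran-Mantel-Haenszel test would add modest power at almost no cost

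*SAP*

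**What the plan says.** SAP 5.6.2.5 (NYHA I/II) and SAP 5.6.2.1 (MR ≤2+) use the same sentence: "Fisher's exact test at the 5% level of significance will be used to compare the proportion of" subjects in each group reaching the endpoint. Neither test has a covariate or a stratum. The one MR sensitivity analysis reclassifies heart failure deaths as 4+ and adjusts for nothing.

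The baseline values are collected:
- **NYHA class.** Protocol 6.5.2 lists, within 14 days before randomization, "An assessment of NYHA Functional Class must be completed".
- **MR grade.** Protocol 6.7 requires, before randomization, that the "Echocardiography Core Lab must confirm MR severity".
- **Planned use.** SAP 5.3 already compares the groups at baseline on "NYHA Class, previous cardiac surgery, prior HF hospitalization, LVEF, left ventricular size, creatinine levels, STS mortality risk score, MR severity".
- **Etiology.** It is a randomization stratum (SAP 5.1).

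For KCCQ, 6MWD and LVEDV the SAP uses ANCOVA on the baseline value. SAP 5.8.4.1 comments that "it is anticipated that an ANCOVA analysis adjusting for baseline values provides as much as or more power than a two-sample" *t*-test.

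On power, SAP 5.8.4.5 says of NYHA: "With the effective sample size of approximate 220 subjects in each arm at 12 months, there is approximate 90% power". SAP 5.8.4.2 gives more than 90% for MR with 300 subjects in total and a difference of at least 20 points. SAP 5.9 says "The secondary endpoints will be tested sequentially in the following order". MR is first of ten tests and NYHA is seventh.

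**The concern.** Fisher's test is conservative, so part of the 5% goes unspent. It also discards baseline information that the SAP uses for its continuous endpoints. For NYHA the omission is easy to see. Entry is "New York Heart Association (NYHA) Functional Class II, III or ambulatory IV", so a class II entrant already meets the I/II endpoint at baseline and baseline class is plausibly prognostic.

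The fixed sequence is what makes power matter here. A miss on MR ends formal testing of the nine tests after it, and a miss on NYHA ends testing of the three after it.

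**Working it through.** **1. Reproduce the plan's figures** (exact enumeration over both binomials, two-sided 5%).
- NYHA, SAP inputs 60% vs 75%, 220 per arm: Fisher power 90.65%, actual size 3.9%. The stated 90% reproduces.
- MR, 20-point difference, 150 per arm (300 split equally): Fisher power 92.91% at 40% vs 60%, 93.35% at 30% vs 50%, 99.10% at 10% vs 30%. Size at 40% is 3.9%. The stated >90% reproduces. The SAP gives no Control MR rate.

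**2. Numbers implied by the SAP's own mortality and attrition inputs.**
- MR: Control 305 × 0.73 × 0.80 = 178, Device 305 × 0.78 × 0.80 = 190. Fisher power at 40% vs 60% is 97.0%, size about 4.4%.
- NYHA, with heart failure deaths (13% and 10%) kept as class IV and other deaths excluded: Control 305 × 0.86 × 0.90 = 236, Device 305 × 0.88 × 0.90 = 242. If 60% and 75% apply to survivors, the rates become 0.73 × 0.60 / 0.86 = 50.9% and 0.78 × 0.75 / 0.88 = 66.5%. Fisher power is 92.7%, size about 4.4%.

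**3. The alternative.** In stratum *k*, let *x* be the Device responders, *m* all responders, *n*₁ and *n*₂ the arm sizes and *T* = *n*₁ + *n*₂. Then E = *n*₁*m*/*T* and V = *n*₁*n*₂*m*(*T*−*m*)/[*T*²(*T*−1)]. The statistic is (Σ(*x*−E))²/ΣV against 3.84, with no continuity correction.

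The strata are baseline grade (NYHA II vs III/IV; MR 3+ vs 4+) by etiology. The documents do not give the following, so they are assumed: 40% class II, 50% MR 3+, 60% ischemic, etiology not prognostic, and the baseline-grade odds ratio (OR) shown. Marginal rates are held at the planned values. There were 100,000 simulated trials per entry, and repeat runs moved entries by about 0.1 to 0.2 point.

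| Power, % | Fisher | CMH, OR 1 | OR 2 | OR 4 | OR 8 |
|---|---|---|---|---|---|
| NYHA 220/arm, 60 vs 75 | 90.7 | 92.1 | 92.6 | 93.9 | 95.6 |
| NYHA 236/242, 50.9 vs 66.5 | 92.7 | 93.5 | 93.9 | 95.3 | 96.9 |
| MR 150/arm, 40 vs 60 | 92.9 | 93.4 | 94.1 | 95.7 | 97.6 |
| MR 178/190, 40 vs 60 | 97.0 | 97.1 | 97.4 | 98.3 | 99.1 |

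At 10% vs 30% and 150 per arm, MR goes from 99.1% with Fisher to 99.4–99.7% with CMH. CMH null rejection was 4.8–5.1%.

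**4. Split the gain.** An unstratified Pearson chi-square shows what comes from leaving Fisher alone.
- NYHA 220/arm: chi-square 92.2%, so 92.2 − 90.7 = 1.5 points come from leaving Fisher. Stratifying adds about 0 at OR 1, 93.9 − 92.2 = 1.7 at OR 4 and 95.6 − 92.2 = 3.4 at OR 8.
- MR 150/arm, 40% vs 60%: chi-square 94.4% (null size 5.2%). Stratifying changes this by 93.4 − 94.4 = −1.0 at OR 1, −0.3 at OR 2 and +1.3 at OR 4. At 30% vs 50% it is −0.4 at OR 1 and about +0.2 at OR 2.
- If the odds ratio of 4 holds in one arm only, CMH gives 92.4–92.7% for NYHA and 94.1% for MR.

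**5. Continuity correction.** With it, NYHA CMH power is 90.3 / 91.0 / 92.5% at OR 1 / 2 / 4, so most of the gain disappears.

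**The case against.** The best defence is that nothing is broken. Fisher guarantees a size of at most 5%, it matches the power calculations in SAP 5.8.4.2 and 5.8.4.5, and exact control is a reasonable choice in a sequence that supports labeling claims. At modest prognostic strength, the gain comes mainly from giving up that guarantee. All of this stands, and it is why the point is minor. It does not defeat the suggestion: the CMH null rejection stayed near 5.0%, and its power was never below Fisher's in the scenarios computed.

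Three stronger readings are tempting and are not supported.
- **That stratifying itself buys several points on both endpoints.** For MR at 150 per arm and 40% vs 60%, plain chi-square beats CMH at odds ratios 1 to 2. Stratifying helps MR only if baseline grade is clearly prognostic, and the documents give no evidence on that.
- **That the SAP contradicts itself.** The ANCOVA remark concerns continuous scores. It sets no rule for binary endpoints.
- **That the labeling sequence is in danger.** The chance of missing MR is 100 − 92.9 = 7.1% only at close to the least favorable rates, the minimum effect and the smaller sample. It is 3.0% at 178/190 and 0.9% at 10% vs 30%. The NYHA gain counts only if six earlier tests succeed. Their planned powers are >90, >90, about 84, >90, about 90 and about 80%. Taking >90 as 90 to 93% and assuming independence, the product is 0.90³ × 0.84 × 0.90 × 0.80 = 0.44 to 0.93³ × 0.84 × 0.90 × 0.80 = 0.49, given primary success. Positive correlation would raise it.

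**Conclusion.** The point holds as a minor, nearly free gain in efficiency. For assumed odds ratios of 1 to 4:
- **NYHA, 220 per arm:** about +1.4 to +3.3 points, conditional on reaching the seventh test. At odds ratios 2 to 4, Fisher would need roughly 18 to 32 more subjects per arm to match.
- **MR:** about +0.5 to +3 points at 150 per arm with a 30–50% Control rate, 0 to 1.3 at 178/190, and under 1 point at a 10% Control rate.

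An odds ratio of 8 would give nearly 5 points on either endpoint (MR at 150 per arm, 40% vs 60%), but nothing in the documents supports assuming it. The text and the direction are certain. The stratification part of the gain rests on baseline shares, odds ratios and a Control MR rate that the documents do not supply. The case is stronger for NYHA, because class II entrants already meet the endpoint. For MR it rests mainly on consistency.

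**What to change.** Before unblinding, amend SAP 5.6.2.5 and 5.6.2.1:
- Make the primary test a CMH test without continuity correction, stratified by baseline grade (NYHA II vs III/IV; MR 3+ vs 4+) and etiology, and state the absence of the correction explicitly.
- Report a Mantel-Haenszel stratified risk difference with 95% CI. In simulation (Sato variance) it averaged 0.150 and 0.200 for true differences of those sizes, with coverage of 94.8–95.2%. The Newcombe interval in SAP 5.7 is described without strata and serves the descriptive endpoints.
- Keep Fisher as a supportive analysis.
- Leave site out of the strata, since many sites may be small. Leave the ANCOVA, joint frailty and Cox analyses as planned.

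The cost is SAP wording, with no new data or visits. Four strata are not sparse: with the assumed shares the smallest holds about 30–35 subjects per arm, or about 18 if only 20% are class II. The one real downside is type I error control that is asymptotic (about 5.0% by simulation) rather than exact.
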